2.2 Objectives

The table below shows the full list of trial objectives and corresponding outcome measures. Objectives in grey will be not analysed by trial statisticians within CSM so are not covered by this SAP.

Primary Objective	Endpoints/ Outcome measures	Time point(s) of evaluation of this end point	Analysis population
To determine the maximum tolerated dose (MTD), and therefore recommended phase II dose (RPTD), of atovaquone when combined with radical concurrent chemoradiotherapy in patients with non-small cell lung cancer (NSCLC)	The dose of atovaquone associated with no more than 48% dose limiting toxicity (DLT) rate (target toxicity level)	From week -2/-3 until three months post-completion of CRT	All patients who have received at least one dose of atovaquone
Secondary Objectives			
To assess the safety and	Adverse events graded per	From screening/baseline until	All patients who have
toxicity profile of atovaquone	Common Terminology	six months post completion of	received at least one dose of
in combination with radical	Criteria for Adverse Events	CRT	atovaquone

concurrent chemotherapy for	(CTCAE) v4.03		
NSCLC	. ,		
To confirm feasibility of measuring hypoxia metagene signature using 3'RNA-Seq in diagnostic NSCLC samples	Hypoxia metagene signature from diagnostic tissue using 3'RNA-Seq	At baseline	
To assess pre-treatment agreement of: 1. FMISO PET-CT with plasma miR-210 level 2. FMISO PET-CT with tumour hypoxia gene expression	 Tumour hypoxic volume determined by FMISO PET-CT Plasma miR-210 level Hypoxia metagene signature from diagnostic tissue using 3'RNA-Seq 	Week -2/-3 (prior to atovaquone treatment)	 All patients with outcome measures from both the baseline FMISO PET-CT scan and the baseline blood sample
To assess agreement in changes in FMISO PET-CT and plasma miR-210 level following two weeks (+/- 7 days) of atovaquone	 Tumour hypoxic volume determined by FMISO PET-CT Plasma miR-210 level 	 Week -2/-3 (prior to atovaquone treatment) Following two weeks (+/- 7 days) of atovaquone treatment 	All patients with outcome measures from FMISO PET-CT scans and blood samples taken at both time points
To assess the tumour response rate at three months following treatment	Response to treatment assessed per Response Evaluation Criteria in Solid Tumours (RECIST) V1.1	Three months post completion of CRT	All patients who commence chemoradiotherapy treatment within the study
Exploratory Objectives			
 To assess the relationship between: 1. plasma atovaquone levels and hypoxia response as measured by FMISO PET- CT 2. plasma atovaquone levels and plasma miR-210 level 	 Plasma atovaquone concentration Tumour hypoxic volume determined by FMISO PET-CT Plasma miR-210 level 	 Week -2/-3 (prior to atovaquone treatment) Following two weeks (+/-7 days) of atovaquone treatment 	 All patients with an outcome measure from the PK assessment and outcome measures from: blood samples taken at both time points FMISO PET-CT scans taken at both time points

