6.1 Patient evaluability and replacement

Patients will not be replaced since the TiTE-CRM uses all accumulated data. However, the TMG may decide to recruit an additional patient if drop-out occurs early in the treatment schedule for reasons other than a DLT. The dose allocated to the additional patient may not necessarily be the same, as this will be determined by the TiTE-CRM model, taking into account accumulated toxicity data at that time point. In the specific situation where one of the first two patients needs to be replaced, the dose allocated to the additional patient will be 450 mg bd, to ensure this dose level is evaluated before escalating to higher doses as per detailed process in section 17.3.

All patients who receive at least one dose of atovaquone will be evaluable for the safety analysis. All patients who commence chemoradiotherapy treatment within the study will be evaluable for response.

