18 STATISTICAL ANALYSIS PLAN

All patients who receive at least one dose of atovaquone, regardless of how much treatment received and follow-up completed, will contribute to analysis. It is therefore important that every effort is made to encourage patients, including those patients who do not receive/complete their allocated treatment, to attend for follow-up clinic visits to avoid bias in the analysis of the results.

A detailed Statistical Analysis Plan will be available from the time the first patient is recruited and will be finalised before any analysis is undertaken. The analysis plan will be written in accordance with the current OCTRU standard operating procedures and will be finalised and agreed by the trial statistician and the CI. Sites must report any unintended deviations to OCTO according to the procedure outlined in site training.

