18.1 Inclusion in analysis

All patients enrolled in the study and who received at least one dose of atovaquone will be accounted for and included in the analyses. The number of patients who were not evaluable, who died or withdrew before treatment began will be recorded. The distribution of follow-up time will be described and the number of patients lost to follow-up will be given.

The analysis will include a description of patients who did not meet all the eligibility criteria, an assessment of protocol deviations, study drug accountability and other data that impact on the general conduct of the study. Baseline characteristics will be summarised for all enrolled patients. Patients who died or withdrew before treatment started or do not complete the required safety observations will be described and evaluated separately. Treatment-related toxicity will be tabulated by type and grade of toxicity. All patients will be evaluable for toxicity from the time of their first treatment. Adverse events will be summarised by the number of patients experiencing each type of event. The grades and causality will be reported.

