unequivocal disease progression] at that time should be reported as "symptomatic deterioration". This is a reason for stopping therapy, but is NOT objective PD. Every effort should be made to document the objective progression even after discontinuation of treatment.

Complete or partial responses may be claimed only if the criteria for each are met at a subsequent time point at least four weeks later. The best overall response can be interpreted from Table B2.

Table B2:	Response	assessment after	subsequent scan
-----------	----------	------------------	-----------------

Response: First time point	Subsequent time point	BEST overall response	Also requires
CR	CR	CR	Normalization of tumour markers All tumour nodes < 10 mm
CR	PR	SD, PD or PR (see comment*)	
CR	SD	SD provided minimum criteria for SD duration met, otherwise, PD	
CR	PD	SD provided minimum criteria for SD duration met, otherwise, PD	
CR	NE	SD provided minimum criteria for SD duration met, otherwise NE	
PR	CR	PR	
PR	PR	PR	
PR	SD	SD	
PR	PD	SD provided minimum criteria for SD duration met, otherwise PD	
PR	NE	SD provided minimum criteria for SD duration met, otherwise NE	
NE	NE	NE	

B.2.1 Frequency of tumour re-evaluation

Response will only be evaluated at one timepoint.

B.2.2 Date of progression

This is defined as the first day when the RECIST (version 1.1) criteria for PD are met.

B.3 Reporting of tumour response

All patients included in the study must be assessed for response to treatment, even if there is a major protocol treatment deviation or if they are ineligible, or not followed/re-evaluated. Each patient will be assigned one of the following categories: complete response, partial response, stable disease, progressive disease, early death from malignant disease, early death from toxicity, early death from other cause or unknown (not assessable, insufficient data).

Early death is defined as any death occurring before the first per protocol time point of tumour re-evaluation. The responsible Investigator will decide if the cause of death is malignant disease, toxicity or other cause.

Patients for whom response is not confirmed will be classified as "unknown", unless they meet the criteria for stable disease (or the criteria for partial response in case of an unconfirmed complete response). Patients' response will also be classified as "unknown" if insufficient data were collected to allow evaluation per these criteria.

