3. STUDY METHODS

3.1 Trial Design/framework

Arcadian is a single arm, open-label phase I dose escalation trial using the Time-To-Event Continual Reassessment Method (TiTE-CRM) i.e. a model-based approach to determine the maximum tolerated dose (MTD) of atovaquone in combination with concurrent CRT in patients with NSCLC.

Patients will receive an oral suspension of atovaquone twice daily. The four atovaquone dose levels to be assessed in the TiTE-CRM is as follows:

Dose level	
1	450 mg
2	600 mg
3	675 mg
4	750 mg

Patients will receive atovaquone alone for 1 to 3 weeks during a run-in period followed by 6.5 weeks of concurrent chemoradiotherapy (CRT). The 6.5 weeks of CRT consists of two cycles: Cisplatin ($80 \text{ mg/m}^2 \text{ IV}$)

on days 1 & 22, Vinorelbine (15 mg/m² IV) on days 1, 8, 22 & 29 and thoracic radiotherapy: 66 Gy in 33 fractions, once daily, 5 days a week (Monday-Friday). Therefore, the total treatment duration is expected to be up to 9.5 weeks.

Patients will have follow-up visits at approximately 1, 3 and 6 months after completion of CRT.

The TiTE-CRM will take into account toxicity from the start of the atovaquone run-in period to 12 weeks (84 days) after completion of CRT, so the end of the toxicity assessment period will be approximately the time of the 3 months post-CRT visit.

The figure below shows the study schema

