Tumour response will be measured according to the RECIST V1.1 criteria, this endpoint will be the response taken at the assessment three months after the completion of CRT (at 13-15 weeks post-CRT).

Response will be classified as complete response (CR), partial response (PR), stable disease (SD), progressive disease (PD) or "not evaluable" (NE), as measured from their baseline scan to three months post-CRT scan. See Appendix 2 of the protocol for response category criteria.

The protocol states 'To be assigned a status of complete response (CR) or partial response (PR), changes in tumour measurements must be confirmed by two observations at least 4 weeks apart.' The Chief investigator has confirmed that it was never the intention for patients to receive a second scan to confirm CR/PR status, furthermore it is not standard of care and it is not included in the MPE dose assessment or IRAS application, so it cannot be done with our current ethics so the disease response will only be taken at the three months post CRT visit. There is currently no plan to update the protocol to amend this minor error.

To be assigned a status of stable disease (SD), tumour measurements must have met the SD criteria at least once, a minimum of six weeks after study treatment is started.

Should rapid tumour progression occur before the completion of treatment, the patient will be classified as having early progression (EP).

Tumour response should be classified as "not evaluable" (NE), only when it is not possible to classify it under another response category (e.g., when baseline and/or follow-up assessment is not performed or not performed appropriately).

Exploratory outcomes

To assess the relationship between plasma atovaquone levels and hypoxia response as measured by FMISO PET-CT and plasma miR-210 level

Plasma atovaquone levels (μ M) will be derived from the pre-CRT blood samples.

Hypoxia response will be measured using TBRvolume (ml) derived from the baseline and pre-CRT FMISO PET-CT scans.

Plasma miR-210 level will be derived from the baseline and pre-CRT blood samples.

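### The response rate counts only patients who start chemoradiotherapy in the study, while Appendix 2 B.3 gives every included patient a response category; patients lost in the run-in can leave the denominator because of their outcome

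*SAP*

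**What the plan says.** **Population.** SAP 2.2 gives the analysis population for tumour response as "All patients who commence chemoradiotherapy treatment within the study". Protocol 6.1 has the matching rule: "All patients who commence chemoradiotherapy treatment within the study will be evaluable for response". The SAP follows the protocol here.

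**Reporting rule.** Protocol Appendix 2 B.3, on reporting tumour response, is wider: "All patients included in the study must be assessed for response to treatment, even if there is a major protocol treatment deviation". It goes on to cover patients who are ineligible or not re-evaluated. Its categories include progressive disease, three kinds of early death (malignant disease, toxicity, other cause) and unknown. It adds: "Early death is defined as any death occurring before the first per protocol time point of tumour re-evaluation". SAP 6.1 refers the analyst to Appendix 2 for the response criteria.

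**General statement.** Protocol 18.1, repeated in SAP 3.7, says: "All patients enrolled in the study and who received at least one dose of atovaquone will be accounted for and included in the analyses". Protocol 18 is similar.

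**Categories.** SAP 6.1 lists CR, PR, SD, PD and NE. The same section then assigns early progression (EP) to rapid progression before treatment is complete, but EP is not in the list. Nor are the B.3 early-death categories.

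**Timing.** SAP 3.1 describes one to three weeks of atovaquone alone before CRT. SAP 3.3 plans 20 evaluable patients, defined as enrolled and given at least one dose of atovaquone.

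**The concern.** A patient is on trial treatment from the first atovaquone dose. If that patient progresses or dies before CRT, B.3 supplies a response category, but SAP 2.2 takes the patient out of the response population. The exclusion happens after treatment has started and can be caused by the outcome being measured. The rate then describes response among patients who got as far as CRT, and it may look better than the rate for everyone given the experimental drug.

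At stake is how the response figure is read if it is later set beside other series or used to plan a phase II trial. Two analysts, one working from SAP 2.2 and the other reporting every patient as B.3 asks, could reasonably present different percentages from the same data.

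**Working it through.** The plan gives no target response rate, power calculation or expected pre-CRT loss for this endpoint, so there is no planned figure to reproduce.

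**Inputs**
- N = 20 dosed patients (SAP 3.3).
- R = responders among CRT starters. This is assumed, from 8 to 14.
- k = dosed patients who never start CRT in the study. This is assumed, from 0 to 4.

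**Step 1. The two rates, with the k patients counted as non-responders.** The CRT-starter rate is R/(20-k) and the all-dosed rate is R/20. Their ratio is 20/(20-k), whatever R is.

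| k | Ratio | CRT starters, R=12 | All dosed, R=12 |
|---|---|---|---|
| 0 | 1.00 | 12/20 = 60.0% | 60.0% |
| 1 | 1.05 | 12/19 = 63.2% | 60.0% |
| 2 | 1.11 | 12/18 = 66.7% | 60.0% |
| 3 | 1.18 | 12/17 = 70.6% | 60.0% |
| 4 | 1.25 | 12/16 = 75.0% | 60.0% |

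Over R = 8 to 14 the gap is 2.1 to 3.7 percentage points at k=1 and 4.4 to 7.8 points at k=2.

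**Step 2. Set against the precision.** The exact (Clopper-Pearson) 95% interval for 12/20 is 36.1% to 80.9%, a width of 44.8 points. For 12/18 it is 41.0% to 86.7%. The shift is small beside either interval.

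**Step 3. How likely is any loss?** If each dosed patient independently fails to start CRT with probability q, the chance of at least one such patient among 20 is 1-(1-q)^20. For assumed q of 2%, 5% and 10% this is 33%, 64% and 88%, with 0.4, 1 and 2 losses expected.

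**Step 4. Direction.** Suppose s of the k excluded patients respond, for instance to CRT given off study. The all-dosed rate is then (R+s)/20. The CRT-starter rate exceeds it when R/(20-k) > (R+s)/20, which rearranges to s/k < R/(20-k). The bias is therefore upward only when excluded patients respond less often than starters. With R=12 and k=2, the starter rate of 66.7% compares with 60.0%, 65.0% or 70.0% for s = 0, 1 or 2.

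**The case against.** The strongest defence is that response among CRT starters is a legitimate, prespecified target. The endpoint is timed at three months after CRT ends, a point that does not exist for someone who never starts. SAP 4.2 sends each secondary endpoint to its own population in SAP 2.2, and Protocol 6.1 is specific to response. B.3 asks for a category for each patient; it states no rate and no denominator, and its set (all included) is not exactly the at-least-one-dose set. SAP 6.2 plans no formal secondary analysis. Losses would remain visible in the CONSORT flow and in withdrawals reported by dose (SAP 5.1, 5.2). All of this stands. It makes the point minor, but it does not remove the mismatch with B.3 or the outcome-related exclusion.

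A reader might also infer four stronger things that the documents do not support:

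- *Everyone who stops for toxicity in the run-in is dropped.* Protocol 8.6 has atovaquone discontinued in that case but does not say that CRT is withheld. A patient who then starts CRT in the study stays in the population.
- *The restriction can only raise the rate.* Step 4 shows that this depends on how excluded patients fare.
- *Protocol 18 directly contradicts SAP 2.2.* Protocol 18 and 18.1 are general statements about contributing to analysis, and dosed patients do contribute to the primary and safety analyses. B.3 is the stronger citation.
- *Early deaths become NE and leave the denominator.* SAP 6.1 reserves NE for patients who fit no other category and refers to Appendix 2, where early death has its own. No passage removes NE patients who started CRT. The incomplete list in SAP 6.1 is a clarity gap and does not exclude anyone.

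**Conclusion.** The concern holds as a minor one. The mismatch lies within the protocol (6.1 against Appendix 2 B.3) and is carried into SAP 2.2; it is not a departure of the SAP from the protocol. Its effect falls only on dosed patients who never start CRT in the study. If they are non-responders, the reported rate is too high, relative to the all-dosed rate, by about 5% for one loss and 11% for two. With no losses there is no effect. The size rests on assumed values of k and R, and the upward direction on excluded patients responding less often than starters. The endpoint is a descriptive secondary one with no decision rule, and it does not enter the MTD.

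**What to change.** 1. Reconcile SAP 2.2 and Protocol 6.1 with Appendix 2 B.3 so that one response population is stated.
2. Report the response rate on all patients given at least one dose of atovaquone. Count as non-response early progression, early death, not evaluable, and never starting CRT in the study without a documented response.
3. Show the CRT-starter rate alongside, with the number of pre-CRT losses and the reasons for them.
4. Add EP and the B.3 early-death categories to the SAP 6.1 list, so that these failures are tabulated apart from missed scans. State that the B.3 definition of early death applies here, since Protocol 13.4 carries a narrower one (first three weeks of treatment, toxic deaths excluded).

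The cost is a wording change and one extra table line, with no new data or patients. The headline rate may come out slightly lower. If the protocol is not to be amended for this alone, SAP 6.1 already records a clarification of the protocol's response rules (on confirmation scans), and the same route could be used.

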3. STUDY METHODS

3.1 Trial Design/framework

Arcadian is a single arm, open-label phase I dose escalation trial using the Time-To-Event Continual Reassessment Method (TiTE-CRM) i.e. a model-based approach to determine the maximum tolerated dose (MTD) of atovaquone in combination with concurrent CRT in patients with NSCLC.

Patients will receive an oral suspension of atovaquone twice daily. The four atovaquone dose levels to be assessed in the TiTE-CRM is as follows:

Dose level	
1	450 mg
2	600 mg
3	675 mg
4	750 mg

Patients will receive atovaquone alone for 1 to 3 weeks during a run-in period followed by 6.5 weeks of concurrent chemoradiotherapy (CRT). The 6.5 weeks of CRT consists of two cycles: Cisplatin ($80 \text{ mg/m}^2 \text{ IV}$)

on days 1 & 22, Vinorelbine (15 mg/m² IV) on days 1, 8, 22 & 29 and thoracic radiotherapy: 66 Gy in 33 fractions, once daily, 5 days a week (Monday-Friday). Therefore, the total treatment duration is expected to be up to 9.5 weeks.

Patients will have follow-up visits at approximately 1, 3 and 6 months after completion of CRT.

The TiTE-CRM will take into account toxicity from the start of the atovaquone run-in period to 12 weeks (84 days) after completion of CRT, so the end of the toxicity assessment period will be approximately the time of the 3 months post-CRT visit.

The figure below shows the study schema

3.2 Randomisation and Blinding

This study is not randomised.

3.3 Sample Size

The sample size will be 20 evaluable patients. Evaluable patients are patients enrolled in the study who received at least one dose of atovaquone.

3.4 Statistical Interim Analysis, Data Review and Stopping guidelines

The TMG will meet following each interim analysis, and as necessary, to review toxicity data and decide on dose escalation.

The first two participants recruited will receive the lowest dose of atovaquone (Dose 1: 450 mg BD). Subsequent eligible patients will be continuously recruited but no dose escalation will be considered until we have at least 12 weeks of safety data for one or both of the first two participants (or at least one participant on dose 1 if the first 2 are not evaluable).

There will be an interim analysis each time a new patient is enrolled. At each interim analysis, the TiTE-CRM model will use all currently available data to recommend the dose to assign the new patient. This analysis will follow the methods for the primary analysis described in Section 6.2. All dose recommendations made by the model will be reviewed by the TMG. The TMG will either approve the dose allocation recommendation or select a lower dose on the basis of clinical review of the data.

In order to escalate to a higher dose of atovaquone, there must be at least one patient on the previous highest dose who fulfils the following criteria:

- Completed ≥1 full cycle of CRT (i.e. at least three weeks of RT)
- Received ≥50% the specified dose of cisplatin
- Taken ≥75% their allocated dose of atovaquone
- Not experienced a DLT

The template for the first TMG dose decision report is given in Appendix 2. Changes may be made to this template as the trial progresses but note that the original template will not be updated as it refers only to the first dose decision meeting.

The TMG will include the Chief Investigator, Co-Investigators, Clinical Trial Manager, Trial Statistician and others as required. TMG membership and decision-making procedures will be documented in the TMG charter.

There is no independent Data and Safety Monitoring Committee (DSMC) for this trial. The Safety Review Committee (SRC) will be convened, as required, to review DLTs and dose escalation decisions made by the TMG. In the event of the TMG being unable to conclude on a dose recommendation, the SRC will meet to decide. The SRC will consist of:

- 1. Trial Statistician
- 2. OCTO trial management representative
- 3. Either:
 - a. One Medical Oncologist and one Clinical Oncologist or
 - b. Two Clinical Oncologists

Additionally, since the window to observe toxicities is long, the TMG may opt to pause recruitment whilst on-trial patients complete their treatment. The trial will stop for safety (i.e. before reaching the maximum number of patients specified by the sample size) if there is sufficient evidence to suggest that the lowest dose is too toxic. More specifically, we will consider dose level 1 (450mg) to be too toxic if, given all the available data, there is more than 70% probability that the DLT rate is greater than the target toxicity level of 48%.

The SRC Charter document for this trial will define the exact membership and who should be present for decisions to be made. Further internal or external experts may be consulted by the SRC, as necessary. Any PI can request an ad hoc SRC meeting at any time in order to facilitate the immediate communication of any emerging safety issues during the course of the trial.

The Independent Radiotherapy and Imaging Oversight Committee (RIOC) will act as the Trial Steering Committee (TSC). The role of RIOC is to provide oversight for the trial on behalf of the Sponsor and Funders. RIOC will provide overall supervision of the safe and effective conduct of the trial, as further defined in the RIOC charter. At least annually, RIOC will review trial progress against agreed milestones, adherence to protocol, and patient safety, and consider new information. RIOC has the authority to recommend study closure where appropriate. Membership of RIOC includes PPI representation.

